**Study Visit 1 and 2:**

Study subjects will arrive at the study site and confirmation of the study subjects' fasting status (minimum 8 hours) will be made. A urine sample will be obtained for a toxic substance screen and for female study subjects, pregnancy testing.

Blood Draws: For all subjects, we will acquire blood samples during Study Visits 1 and 2. The blood draws taken before and after anesthetic exposure will comprise the following: 1.) approximately 2 ml of whole blood for analysis using the 44-analyte TruCultureMAP. Analytes in this map include interleukin 6 and TNF-alpha and, 2.) approximately 13 ml of blood will be acquired processed into serum and stored for downstream studies and

confirmatory assays of TruCultureMAP results.

An EEG montage with a maximum of 256 channels will be placed on the subject. Standard physiological monitors for anesthesia will be placed including: electrocardiogram, pulse oximeter, and non-invasive blood-pressure cuff. End-tidal CO2 measurements will be made by way of a capnogram attached to the expiratory port on the breathing circuit. Galvanic skin response will also be measured. A cuff pain delivery device will be attached to the gastrocnemius area of the lower leg. Baseline vital signs will then be taken. A peripheral intravenous line will be placed and an infusion of ringer's lactate or normal saline will be started. Baseline physiologic measurements will be taken.

The study protocol will be divided into 3 segments. These segments are defined in order as: Baseline Recording; Induction and Recovery from Hypnosis; Post-Anesthesia Recovery.

One time before and one time after the study period, a calibrated cuff pain stimuli will be delivered to the gastrocnemius area of the lower leg using a validated cuff pain device titrated to 8-9/10 pain. A computer controlled air compressor (Hokanson Rapid Cuff Inflator) will inflate the cuff to a pre-specified pressure, and maintain the pressure at that level. Pressure will be maintained for up to 5-minutes to evaluate brain, cardiovascular, and subjective response to experimental pain. One advantage to using cuff algometry pain is that unlike more superficial methods (e.g. heat pain), cuff pain responses are unaffected by sensitization or desensitization of the skin, indicating that this procedure primarily assesses sensitivity in muscle and other deep tissues.

The following questionnaires will be administered during the baseline and recovery periods to assess pain intensity and quality, measure levels of emotional distress and cognitive state.:

- PROMIS Numeric Rating Scale V1.0 – Pain Intensity 1A;
- PROMIS Scale v2.0 – Neuropathic Pain Quality 5a;
- PROMIS Scale v2.0 – Nociceptive Pain Quality 5a.
- PROMIS Item Bank v.1.0 – Emotional Distress-Anxiety Short Form 8A (modified to ask for symptoms experienced within the past hour);
- PROMIS Item Bank v.1.0 – Meaning and purpose Short Form 8A;
- PROMIS Item Bank v.1.0 – Positive Affect Short Form 15A (modified to ask for symptoms experienced within the past hour);
- The Clinician Administered Dissociative States Scale (CADSS)

In addition, inattention, memory and risk assessment cognitive domains will be evaluated using the following three computer presented neurocognitive tasks respectively: 1) Global Precedence, 2) Operation Span and 3) Columbia Card tasks (<https://www.neurobs.com>).

Recording of physiological measurements (blood pressure, heart rate, pulse oximetry, end tidal carbon dioxide, and galvanic skin response) will be initiated and maintained from the beginning of the study protocol until the subject is in the post-anesthesia recovery phase.

The total time under sevoflurane will be approximately the same for both protocols.

During the administration of sevoflurane the subject will be assigned to complete the following auditory task:

Auditory task: Subjects will be asked to respond to auditory stimuli via button-press jittered at random between 4 and 8 second intervals in order to resolve the precise period at which loss and recovery of consciousness/responsiveness occurred at a fine temporal scale. The auditory stimulus will consist of two components, a train of “clicks” and the command “click the mouse”. Subjects will be asked to respond by pressing the mouse in the hand. The sound intensity for all stimuli will not exceed 85 dB sound pressure level (SPL), in accordance with National Institute for Occupational Safety and Health guidelines for occupational noise exposure (U.S. Department of Health and Human Services and National Institute for Occupational Safety and Health, 1998).

Precautions: An experienced board certified anesthesiologist, who is not involved in data acquisition or other study functions will monitor and care for the subject according to the standards for delivery of anesthesia at this institution. The White 5 research unit is equipped with an anesthesia machine, and physiologic data are collected using a Metavision electronic anesthesia record. This research unit has been specifically designed and equipped according to MGH standards and Massachusetts regulations as an anesthetizing location, and it has been approved for this purpose by the Clinical Practices and Safety Committee of the MGH Department of Anesthesia, Critical Care and Pain Medicine. If more care is needed in the judgment of the supervising clinician, the subject may be transferred to the MGH White 3 PACU.

Blood Pressure Management: Decreases in systemic arterial blood pressure are a known, expected side effect of sevoflurane. This is because sevoflurane depresses myocardial contractility and decreases systemic vascular resistance. This is manifested clinically as hypotension, defined as a decrease in mean arterial pressure (MAP) of 15%. Significant decreases in blood pressure caused by sevoflurane will be treated with intravenous phenylephrine. Phenylephrine is a synthetic sympathomimetic drug that selectively stimulates alpha-1 adrenergic receptors. In its clinical use, there is no appreciable effect on beta-adrenergic receptors. Resulting vasoconstriction is greater than arterial constriction. Using an alpha-adrenergic agonist such as phenylephrine to treat hypotension is advantageous because this counters the sevoflurane-induced decrease in systemic vascular resistance. A particular advantage of phenylephrine is that it is usually administered by intravenous infusion and can therefore be easily titrated to effect.

Airway Management: Induction of general anesthesia will cause predictable changes in respiratory function. General anesthetic agents, including sevoflurane, can produce apnea after the loss of consciousness. While the study subject is awake, oxygenation and ventilation will be spontaneous. The standard clinical approach for airway management in surgical patients is for the anesthesiologist to assist oxygenation and ventilation after the loss of consciousness. With progressive loss of consciousness, the study subject will hypoventilate and become apneic. The staff anesthesiologist will use standard airway maneuvers to maintain normal oxygenation and ventilation. These maneuvers include a jaw and chin thrust and assisted ventilation with a mask and bag as part of a circle circuit. Ventilation will be manually assisted as needed. At all times, the inspired oxygen concentration and expired carbon dioxide waveform and partial pressure will be monitored continuously. The minimum inspired oxygen concentration will be 30%. Thus, an anesthesiologist may manually ventilate the subject. The end-tidal (capnogram) carbon dioxide levels will be maintained within 10% of the baseline values. Manually assisted oxygenation and ventilation will continue until the subject recovers spontaneous ventilation.

Post-Anesthesia Recovery: Following Induction and Recovery, the subject will be monitored for post-anesthesia recovery for up to 1 to 2 hours as is done for patients following ambulatory surgery. The subject will be discharged based on established MGH Department of Anesthesia practices for discharge from the hospital following ambulatory surgery. The subject must have stable vital signs, i.e., within 20% of pre-study values, be able to respond appropriately to normal commands, be pain-free, be free from any nausea and vomiting, and have no bleeding from the intravenous site. Subjects must be able to walk unassisted and have an accompanying adult to escort them home. Subjects will be advised not to return to work for 12 hours and be advised against driving or operating heavy equipment for 24 hours.

## **VI. BIostatistical Analysis**

We are using an endpoint of performance score on the Global Precedence task to guide sample size determination. Our null hypothesis is the average within subject difference in performance score for sevoflurane compared to sevoflurane/ketamine is zero. Our

alternative hypothesis is the average within subject difference in performance score for sevoflurane compared to sevoflurane/ketamine is 3. If we assume that the variance in performance score is 9, a type I error of 0.05 and a minimum power of 0.90 for a one-sided z-test, the sample size determinations for our study is 9. Therefore, we should detect a clinically relevant improvement in performance score if we successfully enroll only 9 subjects. To account for data unanticipated events that may lead to poor data quality or data loss, we are proposing to enroll 12 subjects.

EEG acquisition Preprocessing: Continuous EEG will be recorded with up to 256 channels. All data will be stored for subsequent off-line analysis. We will apply an anti-aliasing filter and down-sampled the EEG data to 500 or 250 Hz before analysis. Bandpass filtering of the acquired signal will vary depending upon the features of the EEG data of interest. EEG signals will be remontaged to a nearest-neighbor Laplacian reference, using distances along the scalp surface to weigh neighboring electrode contributions. Trigger signals will be sent from the stimulus delivery system to the EEG recording system to tag the stimulus events for subsequent binning, temporal epoching and averaging of EEG data into the relevant evoked potential averages according to stimulus type and experimental condition.

Video recording to assess level of arousal: Video of the study subject may be recorded during the baseline and induction and recovery from hypnosis periods to assess the study subject's level of arousal. In particular, from clinical experience and previous studies, we note that subjects will exhibit varying levels of arousal after the loss of consciousness, visible in terms of spontaneous movement, which can be recorded on video and then correlated with the EEG. Permission to record video for these data analysis purposes will be obtained from the main research consent form. The video recordings will be stored in a locked file in the investigators office.

Behavioral Analysis: The probability of response to the click and verbal stimuli and the difference in probability of response will be estimated by using Bayesian Monte Carlo methods to fit a state-space model to these data. To perform group-level analyses, we will align the behavioral data across subjects with respect to each subject's LOC time for induction and with respect to each subject's ROC time for emergence. We will then pool the responses within bins. The pooled data will be used to estimate group-level probabilities of response using the state-space model.

Spectral Analysis: We will compute spectrograms for all subjects using the multitaper method. We will also compute group-level baseline-normalized spectrograms for induction and emergence by taking the median across subjects with the data aligned to the LOC and ROC time points, respectively. To determine if the group-level spectrogram is significantly greater than baseline, we will perform a two-group-test as implemented in chronux.

Eigenvalue and Modal Projection Analyses: We will perform an eigenvector decomposition analysis of the cross-spectral matrix to identify the principal modes of oscillation in the conscious and unconscious states and to analyze how activity within these principal modes change through time. We will estimate the cross-spectral matrices  $P_{\text{baseline}}(f)$  and  $P_{\text{unconscious}}(f)$  at each frequency  $f$  using the multitaper method using data from the full baseline period, and segments of at least 5 min extending from LOC to ROC, respectively, for each subject. An eigenvalue decomposition of the median cross-spectral matrix at each frequency will be performed. Each eigenvector describes a

coherent spatial distribution or mode of oscillation, and the corresponding eigenvalue quantifies the power in this mode. We then use modal projection analysis to characterize how power within principal modes change as a function of time. A permutation-based procedure will be performed to assess statistical significance for the modal projection analysis.

Phase–Amplitude Modulation Analysis. We will analyze the relationship between low-frequency phase (0.1–1 Hz) and alpha/beta (8–14 Hz) amplitude by calculating a phase–amplitude histogram. Bandpass filters will be applied to construct narrow-band slow and alpha/beta signals. We will then apply the Hilbert transform to each signal and compute the low-frequency oscillation phase and alpha oscillation amplitude. To construct the histogram, we will assign each temporal sample to one of 18 equally spaced phase bins based on the value of low-frequency oscillation phase, averaging over 2-min epochs. The histogram in each phase bin is the average of alpha oscillation amplitude for all samples within the bin, normalized by the average of alpha oscillation amplitude over the entire 2-min epoch. To assess statistical significance for the histogram, a permutation test will be performed.

Anticipated Findings: Changes in EEG recordings to auditory, somatosensory, may aid principled approaches to brain state monitoring and targeting during general anesthesia.

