### III. SUBJECT SELECTION

We will select 24 volunteer subjects (male and female) between the ages of 18-50 years. The subjects will be recruited using:

- An announcement of the study distributed through the Partners Public Affairs distribution list.

All study subjects will be American Society of Anesthesiologists (ASA) physical status classification P1. That is, all study subjects will be fit and healthy. A complete medical history will be taken and a complete physical examination will be given to rule out active and chronic medical problems.

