**Screening Visit:**

All subjects will complete a screening visit. Study subjects will arrive at the study site to undergo screening to ensure that they meet the basic inclusion/exclusion criteria for the study and give written informed consent. All questions will be explained as needed. All women of childbearing age will be tested for pregnancy. A urine hCG pregnancy test will be performed. If the test performed comes back negative for pregnancy, the subject will be enrolled. If the test performed comes back positive for pregnancy or the subject is breastfeeding, the subject will not be enrolled in the study. If the test performed comes back borderline, we perform another test.

Consent Procedures: Prior to the study, each subject will sign an informed consent form. The investigator obtaining consent will explain in detail the protocol of the study, its purpose and potential benefits to the society. Subjects will be informed that if they feel uncomfortable with the study, they can choose to terminate the study at any time.

Physical Examination: The subjects will be given a standard pre-anesthetic physical examination. Particular attention will be paid to the subject's airway anatomy and neurologic function. Any abnormal findings on physical examination will be reason for exclusion from the study. Abnormal findings will be reported to the subjects and recommendations for medical follow-up will be given as needed.

Screening Tests: A complete blood count, blood glucose level, liver function tests (LFTs), blood urea nitrogen (BUN), and creatinine (Cr) level will be obtained at the initial screening visit. For inclusion into the study protocol, each subject will be required to have a platelet count, blood glucose, BUN levels, Cr levels, white blood cell count, hemoglobin, differential and LFTs within 2 times the upper and lower limit of normal. Any subject who tests positive for any "street drugs" (amphetamine, barbiturates, benzodiazepines, cannabinoids, cocaine, opiates, or phencyclidine) may be excluded from the study. An ECG will also be performed.

Randomization: Visits 1 and 2 will be randomized to determine their order of occurrence: sevoflurane only vs. sevoflurane with ketamine.

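### Low-cost improvement: no balancing of visit order is described and the only stated Global Precedence comparison has no visit term; blocked order plus a visit term would protect this small crossover

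*Combined protocol and SAP*

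**What the plan says.** Under Screening Visit in Section IV, the randomization text is one sentence: "Visits 1 and 2 will be randomized to determine their order of occurrence", the two conditions being sevoflurane alone and sevoflurane with ketamine. It mentions no blocks, fixed sequence split or other balancing method, and does not say how each subject's order is drawn.

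Section VI introduces the score as a sizing device: "We are using an endpoint of performance score on the Global Precedence task to guide sample size determination". The null hypothesis is that "the average within subject difference in performance score for sevoflurane compared to sevoflurane/ketamine is zero"; the alternative is a mean difference of 3. The variance is 9, the type I error 0.05, and the requirement is "a minimum power of 0.90 for a one-sided z-test". The result is 9 subjects, with 12 to be enrolled to allow for data loss. Section III gives another total: "We will select 24 volunteer subjects (male and female) between the ages of 18-50 years". That discrepancy is a separate matter, so both totals are used below.

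The task is one of "three computer presented neurocognitive tasks respectively: 1) Global Precedence, 2) Operation Span and 3) Columbia Card tasks", listed in the procedures headed "Study Visit 1 and 2", so it belongs to both visits. The rest of Section VI analyses other data: "The probability of response to the click and verbal stimuli", spectra, modal projections and phase–amplitude coupling. None of those paragraphs mentions the Global Precedence score or a visit, period or sequence term.

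**The concern.** A computer task done at two visits may be done better the second time. In a two-visit crossover, that shift adds to the treatment difference for subjects who have ketamine second and subtracts from it for those who have ketamine first.

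Randomised order makes the shift cancel on average, but not in the one split that occurs. With 9 to 12 subjects an uneven split is common. The unadjusted mean difference then carries part of the visit effect, in a direction set by chance. Even with an even split, a paired t-test without a visit term leaves the visit effect in its error variance and loses power. Both problems can be removed at the design stage almost for free.

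**Working it through.** **Inputs from the documents:** target difference 3, variance 9, one-sided type I error 0.05, power 0.90, n = 9, enrolment of 12 (Section VI) or 24 (Section III).

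**Assumptions not in the documents:** each subject's order is drawn independently (simple randomisation); the visit 2 minus visit 1 shift π is 1, 1.5 or 3 points, where 3 is an extreme case equal to the whole target effect.

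**1. The plan's own figure.** n = (1.645 + 1.282)² × 9 / 3² = 8.56, rounded up to 9. It reproduces when 9 is taken as the variance of the within-subject difference. The z-test has power 0.912 at n = 9 and 0.966 at n = 12.

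**2. Model.** d = T + sπ + e, with s = +1 or −1 by order. The unadjusted mean is shifted by π(n1 − n2)/n.

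**3. How uneven the split may be.** For 12 subjects, P(6:6) = 924/4096 = 0.226 and P(8:4 or worse) = 0.388. At 8:4 the shift is π × 4/12, that is 0.33, 0.50 or 1.00 points. For 24 subjects, P(16:8 or worse) = 0.152.

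**4. Power and error if 9 is the residual variance, so the visit effect adds to it.** True difference 3; paired t by simulation, z-test by exact sum over binomial splits with its variance held at 9.

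| n = 12 | π = 1 | π = 1.5 | π = 3 |
|---|---|---|---|
| Paired t, simple randomisation: power | 0.924 | 0.895 | 0.738 |
| – type I error | 0.05 | 0.05 | 0.05 |
| z-test, simple randomisation: power | 0.958 | 0.948 | 0.900 |
| – type I error | 0.059 | 0.071 | 0.123 |
| Paired t, 6:6, no visit term: power | 0.93 | 0.914 | 0.795 |
| – type I error | 0.042 | 0.033 | 0.010 |
| t with visit term, 6:6: power | 0.942 | 0.942 | 0.942 |
| – type I error | 0.05 | 0.05 | 0.05 |

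The z-test error rises because its statistic has variance 1 + π²/9 rather than 1. For π = 3, 1.645/√2 = 1.163, a tail of about 0.12 at any n.

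At n = 24 the paired-t power is 0.998, 0.996 and 0.959, and the z-test power 0.999, 0.998 and 0.989. The z-test error is unchanged to within rounding.

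**5. If 9 is already the total variance under randomised order.** The residual variance is 9 − π² = 8 for π = 1 and 6.75 for π = 1.5. At n = 12 the unadjusted analysis keeps its stated properties: t power about 0.945, z power 0.966, error 0.05. The 6:6 split with a visit term raises t power to 0.961 and 0.981.

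**6. Cost when there is no visit effect.** The adjusted standard error is (3/2)√(1/n1 + 1/n2). At 6:6 it is 0.866, equal to 3/√12, so only a degree of freedom is lost.

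| Evaluable, split | Paired t | t with visit term |
|---|---|---|
| 12, 6:6 | 0.945 | 0.942 |
| 12, 8:4 | 0.945 | 0.918 |
| 9, 5:4 | 0.862 | 0.849 |
| 9, 6:3 | 0.862 | 0.815 |

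**The case against.** The strongest reply is that the target is a sizing formula. Such formulas usually leave out nuisance terms, and no hypothesis in Section II concerns this score. That is fair: the silence does not show that the final analysis will omit a visit term. But the plan gives no other analysis of the score, so stating the model now closes the gap.

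A reader might infer that the order will be unbalanced. The documents do not support that; they are silent on the method. If the allocation list is in fact blocked, the chance shift and the z-test's excess error disappear, apart from imbalance caused by dropout.

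A reader might also infer that the estimate is biased or that the stated power is wrong. Neither follows. Random order keeps the estimate unbiased on average, n = 9 reproduces, and the z-test at 12 subjects still has power 0.900 at a visit effect of 3. The error of 0.123 comes from fixing the variance at 9 when the assumed model makes it 18; the paired t-test keeps 0.05.

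A same-visit baseline could absorb part of a practice effect. Section IV sets the questionnaires at baseline and recovery and then adds the tasks without separate timing. The tasks may therefore also be run at baseline, but the plan does not define the score as a change.

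Finally, the visit term can cost power. With 9 evaluable subjects at 6:3 it gives 0.815, while the unadjusted paired t under simple randomisation has 0.862 with no visit effect and 0.828 with a 1-point effect. That stands and is counted in the cost.

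**Conclusion.** The point holds as a low-cost improvement. At 12 subjects, with independent draws of order and 9 as residual variance, an unadjusted paired t-test loses about 0.02 of power at a 1-point visit effect (0.945 to 0.924) and 0.05 at 1.5 points (0.945 to 0.895). The fall to 0.738 needs a visit effect as large as the target effect and should be read as an outer bound. If 9 is the total variance, there is no loss against the stated figures, only power that could be gained. At 24 subjects the power effect is small.

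The firmest part does not depend on how 9 is read: under independent draws, 8:4 or worse occurs in 39% of trials of 12, and at 8:4 a third of any visit effect enters the estimate. The size of that effect is unknown.

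**What to change.** Allocate visit order in balanced blocks, ending at 6:6 for 12 subjects or 12:12 for 24. State in Section VI that the within-subject Global Precedence difference will be estimated as the average of the two sequence means (a visit-order term) and tested by a t-test on n-2 degrees of freedom. Say also whether the task is run at each visit's baseline and whether the score is a change from it.

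Make both changes together if a t-test is used: blocking alone leaves the visit effect in the error variance, and the visit term without blocking averages 0.919 power at 12 subjects. If the fixed-variance z-test were kept, a 6:6 split alone would give power 0.966 and error 0.05.

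The cost is an allocation list and a few sentences, with no added subjects or procedures. With no visit effect, t power goes from 0.945 to 0.942 at 6:6. If only 9 subjects are evaluable it goes from 0.862 to 0.849 at 5:4 or 0.815 at 6:3, because blocking does not guarantee balance among completers. The change does not bring a t-test to 0.90 power at 9 subjects, where it has 0.862 even without a visit effect.

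### The stated minimum power of 0.90 with 9 subjects holds only if the variance is known; with the SD estimated, power at 9 is about 0.86 and 11 evaluable subjects are needed

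*Combined protocol and SAP*

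**What the plan says.** Section VI of the combined protocol and SAP contains the only sample size calculation in the documents.

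- Endpoint: "We are using an endpoint of performance score on the Global Precedence task to guide sample size determination".
- Null: "Our null hypothesis is the average within subject difference in performance score for sevoflurane compared to sevoflurane/ketamine is zero".
- Alternative: "alternative hypothesis is the average within subject difference in performance score for sevoflurane compared to sevoflurane/ketamine is 3".
- Variance: "If we assume that the variance in performance score is 9". No source or pilot estimate is given.
- Type I error: "a type I error of 0.05".
- Power, test and result: "a minimum power of 0.90 for a one-sided z-test, the sample size determinations for our study is 9", from which the plan concludes that "we should detect a clinically relevant improvement in performance score if we successfully enroll only 9 subjects".

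The same paragraph proposes enrolling 12, the extra three being an allowance for poor or lost data. The rest of Section VI covers EEG, video and behavioural response data. It names no test for comparing the Global Precedence score between conditions and does not say how the variance will be handled. Section IV (Randomization) makes the design a two-visit crossover with randomized order, so each subject contributes one difference.

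**The concern.** A z-test needs a variance fixed in advance. Section VI assumes a value for planning, but nothing says that this value will be imposed in the analysis. Ordinarily the SD would be estimated from the observed differences. With 9 differences there are 8 degrees of freedom, and the statistic follows a t distribution (for normal differences). The normal cut-off is then too lenient, and the correct t cut-off costs power.

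Two statements are at stake: that power is at least 0.90 at 9 subjects, and, by implication, that three of 12 subjects can be lost with the target still met. Losses are foreseeable, because each subject must complete two anesthesia visits and Section III (Remuneration) provides for those who complete only one. A team relying on the text could accept three losses in the belief that the planned power was intact.

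**Working it through.** **Inputs (Section VI).** Mean difference δ = 3; variance 9, so SD σ = 3; one-sided α = 0.05; power at least 0.90. The variance is first taken as that of the within-subject difference, because this reproduces the plan's result.

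**1. The plan's own figure.** n = [σ(z₀.₉₅ + z₀.₉₀)/δ]² = [3 × (1.645 + 1.282)/3]² = 8.56, rounded up to 9. Known-variance power at 9 is Φ(√9 × 3/3 − 1.645) = Φ(1.355) = 0.912. The stated 9 reproduces.

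**2. SD estimated, t cut-off.** Power = P[T > t₀.₉₅(n − 1)], where T is noncentral t with n − 1 degrees of freedom and noncentrality √n × δ/σ = √n. The fourth column is step 3.

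| Evaluable n | t cut-off | Power, t-test | Type I error if 1.645 is used with an estimated SD |
|---|---|---|---|
| 9 | 1.860 | 0.8618 | 0.0693 |
| 10 | 1.833 | 0.8975 | 0.0672 |
| 11 | 1.812 | 0.9245 | 0.0655 |
| 12 | 1.796 | 0.9447 | 0.0641 |
| 24 | 1.714 | 0.999 | 0.0568 |

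The smallest n with power of at least 0.90 is 11.

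**3. SD estimated, z cut-off kept.** At n = 9, power is 0.9035, but the type I error is P(t₈ > 1.645) = 0.0693 instead of 0.05.

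A simulation of 1,000,000 data sets at n = 9 gave 0.8625 for the t-test power and 0.0696 for the type I error of the z cut-off.

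**4. Loss allowance.** The plan implies 12 − 9 = 3. With the t-test it is 12 − 11 = 1.

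**5. The other reading of the variance.** If 9 is the variance of a single score, the variance of the difference is 2 × 9 × (1 − ρ) = 18(1 − ρ), where ρ is the within-subject correlation. The documents do not give ρ; the values below are assumptions.

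| Assumed ρ | Variance of difference | t-test power at 9 | t-test power at 12 |
|---|---|---|---|
| 0 | 18 | 0.615 | 0.742 |
| 0.25 | 13.5 | 0.723 | 0.842 |
| 0.5 | 9 | 0.862 | 0.945 |
| 0.75 | 4.5 | 0.986 | 0.998 |

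The type I error of 0.069 in step 3 does not depend on the variance.

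**The case against.** The strongest reply is that the plan names its test and states its assumption, and on those terms 9 is right. That stands: there is no arithmetic error, and the shortfall is conditional on the SD being estimated. A reader might infer that the trial cannot have both a type I error of 0.05 and power of 0.90 at 9 subjects. The documents do not support that as an unconditional statement. Under the z-test as named it has both, and no section says that the SD will be estimated, although imposing an unsourced variance in the analysis would be unusual.

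The second reply is that enrolment of 12 already covers the gap. This is largely true: power is 0.9447 with 12 evaluable and 0.9245 with 11, and at 10 it misses the target by only 0.0025. A reader might infer that the trial is underpowered as designed. On the variance reading that reproduces 9, it is not. What remains wrong is the statement about 9 and the size of the loss allowance.

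Third, Section III gives 24 subjects, and 24 evaluable would give power of 0.999 on the same inputs. Section VI nevertheless proposes 12. The conflict is a separate matter and does not alter the result at 9. Equally, this point cannot be used to endorse either enrolment figure.

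Fourth, the meaning of the variance matters more than the choice of z or t. Over the assumed correlations, power at 9 runs from 0.615 to 0.986. This stands, and the figures 86% and 94% should not be quoted without that condition.

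Last, a simple paired t-test is not the only reasonable choice, since visit order is randomized. A period-adjusted analysis with n − 2 degrees of freedom gives 0.849 at 9 (sequences of 4 and 5) and 0.942 at 12 (6 and 6), on the same inputs. The conclusion is the same, so the specific t-based test can be left to the investigators.

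**Conclusion.** The point holds in conditional form, at moderate severity, as a methods error in the stated power. If the SD is estimated, the differences are roughly normal, and 9 is the variance of the within-subject difference, then 9 evaluable subjects miss the plan's own minimum. The chance of missing the assumed effect is about 14% (1 − 0.862) against a stated maximum of 10%. Keeping the normal cut-off instead raises the type I error by 0.019 (0.069 against 0.05). Which of the two applies depends on an analysis that the documents do not specify. The practical consequence is confined to the loss allowance, which is one subject out of 12 and not three.

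**What to change.** In Section VI:

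1. Replace the z-test with a t-based test on the within-subject differences, and state that the same test will be used to analyse the Global Precedence score.
2. State that 9 is the variance of the within-subject difference and give its source. If it is the variance of a single score, give the assumed correlation, compute 18(1 − ρ) and redo the calculation.
3. If the variance of the difference is confirmed as 9, restate the power for a one-sided paired t-test at 0.05: 86% with 9 evaluable subjects, 94% with 12, and 11 evaluable needed for at least 90%. If a period-adjusted test is chosen, use its slightly lower figures.
4. Replace the sentence saying that 9 enrolled subjects suffice with one requiring 11 subjects with evaluable data from both visits, and describe the margin in 12 as one subject.

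The cost is the rewording of one paragraph and a less favourable power figure at 9. No subjects need to be added if 9 is the variance of the difference; under the single-score reading with a low correlation, 12 would fall short. The 12 in Section VI and the 24 in Section III must be reconciled separately.
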